Recently, the FDA issued warning letters to online retailers for marketing CBD with false claims and illegally promoting it as a drug for a variety of medical conditions, including preventing Alzheimer's disease, curing cancer and relieving chronic pain.¹⁴ This is a public health concern, as these types of claims may be influencing consumers to use CBD, often in combination with other medications and without medical supervision, putting consumers at undue risk. While these claims have been documented online, the point-of-sale at brick and mortar retailers, where the majority of consumers purchase CBD,¹⁰ has been largely ignored. **No studies have documented CBD health claims at the point-of-sale.** Furthermore, there is substantial

evidence that retail advertising influences consumer perceptions and behaviors for other substances (e.g. tobacco, food), but no such evidence exists for how CBD health claims impact consumer behavior.

Therefore, the objective of our study is to inform regulatory science by documenting CBD health claims in brick and mortar retailers, evaluate consumer perceptions of them, and evaluate their impact on consumer purchase behavior.

Objective(s)

The overarching goal of this web survey is to assess consumer claim perceptions and claim meanings of CBD advertisements documented in a sample of brick and mortar retailers in North Carolina, Maryland, and Colorado, as well as willingness to try, perceived product safety, perceived benefits, and outcome expectancies.

Online Consumer Perceptions Survey PROTOCOL

Methods and Measures

Design

We will conduct a cross-sectional online survey with a nationally representative probability-based sample of adults (ages 18-65) recruited from the AmeriSpeak panel, funded and operated by NORC at the University of Chicago. All panel members aged 18-65 will be invited to be screened, and those who have used CBD in the past 30 days (current users), those who have ever used CBD (ever), and those who have never used CBD (non-users) will be invited to participate. We will assess consumer perceptions of documented health claims made inside CBD retailers. Given NORC's estimated response rate of 34% and prevalence estimates for CBD use between 14-25%, we estimate a random sample of 22,000 adults will be screened to achieve our goal of 3,000 completed surveys consisting or 1,000 current CBD users, 1,000 ever CBD users, and 1,000 non-users. AmeriSpeak participants will receive points, worth approximately \$5, for completing the survey. No incentive will be provided for completing the screener. Although our goal is to have 3000 completed surveys, we anticipate having up to 600 additional completed surveys since this is an online survey and we will allow anyone who is taking the survey to complete it and receive the incentive. We will monitor the number of completed surveys by user status on a daily basis to achieve the targeted goal of 3000 completes and minimize additional surveys over the targeted goal. Thus, our sample size is n=3525. We will assess data quality by ensuring participants meet sufficient completion criteria. Participants must have met both of the following criteria to be included in the study: 1) at least 75% of the outcome variables answered (not skipped) and 2) survey completion time of > 5min. All completed surveys will be used in data analysis.

To assess eligibility, participants will be asked their age and several questions about CBD use. If eligible, participants will be invited to complete the full survey. For the survey, participants will be randomly assigned to a panel consisting of up to 10 CBD advertisements that include FDA prohibited or potentially-prohibited claims. Participants will complete questions while the stimuli are shown on the survey webpage. After the interview, participants will receive a link to electronic resources with up-to-date CBD information based on the literature, guidance documents from the Food and Drug Administration (FDA), and organizations including the Center for Disease Control (CDC) and Substance Abuse and Mental Health Services Administration (SAMHSA).

Setting

Survey participants will complete the online survey in a location of their choosing.

Subjects Selection Criteria

AmeriSpeak is an active panel, funded and operated by NORC at the University of Chicago that is designed to be representative of the U.S. household population. U.S. households are randomly selected within NORC's National Sample Frame and supplemented by address-based sample frames. This is conducted through a two-stage sampling process. The first stage is the primary sampling unit, which is a National Frame Area of an entire metropolitan area or county. The second stage occurs within this sampling unit. Secondary sampling

units are segments defined from Census tracts or block groups. Within these segments, all housing units are listed using the U.S. Postal Service Delivery Sequence File. The final National Frame contains approximately 3 million households. Selected households are invited to join AmeriSpeak™ by telephone or by web, and participate in research studies 2-3 times a month. For this study, all 18-65 year old panel members will be screened by AmeriSpeak™. Individuals who are a current CBD user within the past 30 days will be invited to participate in the study. We will also include a sample of ever-CBD and non-CBD users to understand consumer perceptions from those who do not currently use, as well. We will oversample CBD users so the final respondent sample is comprised of 1/3 current CBD users, 1/3 ever CBD users, and 1/3 never-users. It is expected that AmeriSpeak™ will screen 22,000 adults to obtain the sample size.

(Approximately 1,000 current CBD users; 1,000 ever CBD users, and 1,000 non-users). Therefore, the survey will begin with a short screener survey about CBD use.

Screener

All interested individuals will be able to complete our screener. Interested individuals will click on the link to the survey and be routed to a website to review consent language and complete the survey. Participants will complete a one-minute screener to determine if they are eligible for the full survey based on their age and CBD use. If eligible, they will be consented and then proceed to take the survey.

Inclusion Criteria

- Age 18-65
- US Residents

Exclusion Criteria

- Non-English speakers
- Younger than 18 or older than 65
- Not US residents

Full Survey

Inclusion Criteria

- Age 18-65
- US Residents
- Satisfies one of the following categories:
 - o 1. Current CBD users
 - o 2. Ever CBD users
 - o 3. Non-CBD users
- Members of the AmeriSpeak[™] panel

Exclusion Criteria

- Non-English speakers
- Younger than 18 or older than 65
- Not members of the AmeriSpeak[™] panel

Sample Size

Based on a response rate of 34% and prevalence estimates for CBD use between 14-25%, we
estimate a random sample of about 22,000 adults will be invited to complete the screener survey to
achieve our goal of 3,525 completed surveys.

Interventions and Interactions

Individuals will be contacted by AmeriSpeak™ to participate in the survey, and if interested, will complete a screener to determine eligibility. After completing the screener, participants who are ineligible will be thanked for their time and will exit the survey. They will not receive an incentive for completing the screener. Participants who meet eligibility criteria will be invited to complete the full survey. The full survey will last

approximately 15-20 minutes. After completing the survey, participants will receive a small incentive in the form that they've agreed to with their panel (approximately \$5).

Outcome Measure(s)

Outcome Measure

This is a post-test only experimental design. The primary outcome is *claim perception* by CBD use status. We will determine if advertisements are interpreted by consumers in one or more ways that the FDA has determined are prohibited (i.e. drug effect; FDA approved/endorsed; dietary supplement; food additive; false/misleading-youth; false/misleading-science). We will assess this using the following items, all of which will use a 5-point response scale, (1) Not at all to (5) Extremely.

To assess drug effect claims, all participants will be asked "How much does this ad suggest that CBD can cure, prevent, or treat a health condition?"

To assess FDA endorsement claims, participants will be asked "How much does this ad suggest that the advertised CBD is approved or endorsed by the US Food and Drug administration (FDA)?"

To assess dietary supplement or vitamin claims, participants will be asked "How much does this ad suggest that CBD is a dietary supplement or vitamin?"

To assess food additive claims, participants will be asked "How much does this ad suggest CBD is a main ingredient in a food or beverage?

To assess if a claim is false and misleading participants will be asked "How much does this ad suggest the information shown is based on scientific evidence?" and "How much would this ad appeal to youth under the age of 18?"

We will also assess perceived product safety, appealand perceived benefits, outcome expectancies, and willingness to try CBD (non-CBD users only). For CBD users, we will ask additional questions about their use of CBD (i.e. frequency, product type, reasons for use, and use with other cannabinoids). All participants will be asked about their demographic and health status.

Analytic Plan

The goals of the analysis are to 1) determine if CBD use status is associated with interpreting our main outcome and secondary outcomes (main = claim perception as one of the prohibited claim types, secondary = appeal of advertisements and perceived product safety); 2) identify which claims are interpreted by consumers in ways that the FDA has determined are prohibited; and 3) explore participant characteristics (beyond use status) that are associated with interpreting a claim as one of the prohibited claim types.

First, analyzing all claims together, we will assess the mean score for each claim type (i.e. drug effect; FDA approved/endorsed; dietary supplement; food additive; false/misleading-youth; false/misleading-science) to determine if CBD use status is associated with interpreting ads as containing one of the prohibited claim types. We will also assess the mean for perceived product safety and appeal by use status. For each of the advertisements, we will then estimate the proportion of participants that interpret the claim as one or more of the prohibited claim types (i.e. drug effect, FDA approved/endorsed; dietary supplement; food additive; false and misleading). Chi-squared tests will compare proportions between CBD users and non-users. Next, analyzing all claims together, we will model the likelihood of interpreting a claim as a prohibited claim type as a function of CBD use status, sex, race/ethnicity, claim meaning score, and chronic health conditions using random-effects logistic regression modeling to account for the repeated measures within an individual. Odds ratios from the models will be used to identify differences between groups in their perceptions of claims. All statistical tests will be two-sided with a 0.05 significance level and all analyses will be performed using SAS V9.4.

Human Subjects Protection

Subject Recruitment Methods

Participants will be recruited and screened by AmeriSpeak™ according to age (18-65) and CBD use status (current CBD (users within the last 30 days), ever CBD users, and non-users). All panel members who are 18-65 years old will be screened for the survey, and those who are classified as a CBD user, ever user, or non-user will be invited to participate in the study. Eligible participants will continue to review the informed consent and complete the full survey.

Informed Consent

A waiver of signed consent/assent s requested. This is an online survey and individual participation involves providing voluntary responses to survey questionnaires. The research presents no more than minimal risk of harm to subjects. Consent language will be included in the survey and participants will be asked to check a box to indicate that they agree to participate.

Confidentiality and Privacy

Confidentiality will be protected by collecting only information needed to assess study outcomes, minimizing to the fullest extent possible the collection of any information that could directly identify subjects, and maintaining all study information in a secure manner. Data will be collected and housed on the secure NORC server and the Wake Forest University School of Medicine server. De-identified data will be provided to the Wake Forest team.

Access to de-identified data will be limited to study staff. Data and records will be kept locked and secured with any computer data password protected. No reference to any individual participant will appear in reports, presentations, or publications that may arise from the study.

Data and Safety Monitoring

The Principal Investigator, [name] will be responsible for the overall monitoring of the data and safety of study participants. [name] will be assisted by other members of the study staff. It will also be monitored closely by the Wake Forest School of Medicine IRB.

Reporting of Unanticipated Problems, Adverse Events or Deviations

Any unanticipated problems, serious and unexpected adverse events, deviations or protocol changes will be promptly reported by the PI or designated member of the study team to the IRB and sponsor or appropriate government agency if appropriate.

References Cited

- 1. National Academies of Sciences, Engineering, and Medicine. *The Health Effects of Cannabis and Cannabinioids:The Current State of Evidence Recommendations for Research.* Washington (DC)2017.
- 3. US Congress. Agriculture Improvement Act of 2018. In. Pub. L. 115-334Dec. 20, 2018.

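### Random assignment to ad panels is not tied to CBD use status, although status is known beforehand and defines the primary comparison; assigning within status is a small gain that needs no extra respondents

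*Combined protocol and SAP*

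**What the plan says.** The Design section gives the whole assignment rule: "participants will be randomly assigned to a panel", which it describes as "a panel consisting of up to 10 CBD advertisements". It names no stratification factor, no blocking, no quota per panel, no number of panels and no target number of raters per ad.

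Use status is collected first. The Design section says "To assess eligibility, participants will be asked their age and several questions about CBD use", and the Screener section says "Participants will complete a one-minute screener to determine if they are eligible for the full survey based on their age and CBD use". The target is "1,000 current CBD users, 1,000 ever CBD users, and 1,000 non-users". The control described over those totals is by group, not by panel: "We will monitor the number of completed surveys by user status on a daily basis".

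The Outcome Measure section makes claim perception by use status the primary outcome. In the Analytic Plan, mean scores pooled over all ads are compared by status, and at ad level "Chi-squared tests will compare proportions between CBD users and non-users". A pooled random-effects logistic model then includes status among its covariates. Its random effects handle repeated ratings by the same person, and no ad or panel term is listed.

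**The concern.** The plan oversamples to obtain thirds by use status, but the written text does not control how each third is spread over the panels. Under simple randomisation two things follow.

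- **Single ads.** Some ads will be rated by fewer users or fewer non-users than others, for no design reason. The user versus non-user tests for those ads are less precise.
- **The pooled contrast.** One status group may, by chance, see a somewhat different mix of ads from another. If ads differ in how strongly they suggest a prohibited claim, this adds noise to the pooled difference between groups. A model without an ad or panel term does not remove it.

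The stratifying variable is in hand before assignment, so both effects are avoidable.

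**Working it through.** The documents give no power, effect size or raters-per-ad figure, so there is no stated figure to reproduce on this point. The check is what simple randomisation would cost compared with exact balance within status.

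**Inputs.** N per status group is 1,000 (the Design target), or 3,525 / 3 = 1,175 (the stated sample size, if split in thirds). The number of panels K is not given and is varied. Further assumptions: panels equally likely, and each ad in one panel only.

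**Step 1: raters per ad and group.** The count is Binomial(N, 1/K), with mean N/K and SD √[N(1/K)(1 − 1/K)]. For N = 1,000:

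- K = 10: mean 100, SD √(1,000 × 0.1 × 0.9) = 9.5, 95% range 82-119.
- K = 20: mean 50, SD √(1,000 × 0.05 × 0.95) = 6.9, 95% range 37-64.
- K = 50: mean 20, SD √(1,000 × 0.02 × 0.98) = 4.4, 95% range 12-29.

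For N = 1,175 and K = 10: mean 117.5, SD 10.3, range 98-138.

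**Step 2: variance of an ad-level difference.** The variance is proportional to 1/n₁ + 1/n₂, and the balanced value is 2K/N. The ratio of the two was simulated with multinomial allocation of two groups. A first-order approximation to its mean is 1 + (K − 1)/N. For example, K = 10 and N = 1,000 give 1 + 9/1,000 = 1.009. The worst-panel column is the average, over simulated allocations, of the square root of the largest ratio. The smallest cell is the average minimum over the 2K cells.

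| K | Mean variance increase (N = 1,000; 1,175) | Worst-panel CI wider by (N = 1,000; 1,175) | Smallest cell (N = 1,000) |
|---|---|---|---|
| 2 | 0.1%; 0.1% | 1%; 1% | 482 |
| 5 | 0.4%; 0.4% | 3%; 3% | 180 |
| 10 | 0.9%; 0.8% | 6%; 6% | 82 |
| 20 | 2.0%; 1.7% | 12%; 10% | 36 |
| 40 | 4.3%; 3.6% | 22%; 19% | 14 |

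**Step 3: power for one ad.** Take N = 1,000, two-sided 0.05, one group at 50%, and a difference chosen to give about 80% power at exact balance. Average power under simple randomisation is 0.798 for K = 10, 0.793 for K = 20 and 0.782 for K = 50. The loss is under one point up to K = 20 and about two points at K = 50. Averages hide the spread: 95% of draws give 0.74-0.85, 0.71-0.86 and 0.62-0.90 respectively.

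**Step 4: the pooled contrast of mean scores.** Let τ be the SD of panel means and σ the within-panel SD of person means, both on the 1-5 scale. The variance of a group mean is (τ² + σ²)/N under simple randomisation and σ²/N when panels are balanced within status. The removable share is τ²/(τ² + σ²), whatever K is. The documents give neither SD. Assuming σ = 0.8:

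- τ = 0.1: 0.01/0.65 = 1.5%
- τ = 0.2: 0.04/0.68 = 5.9%
- τ = 0.3: 0.09/0.73 = 12%

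**The case against.** **The text is silent, not wrong.** A reader might infer that nothing balances the panels. The documents do not support that: least-filled or quota assignment would also fit the one sentence given. What can be said is that the method is unstated and that no link to use status is written down. This objection stands.

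**Not every analysis is by status.** A reader might also infer that all analyses are status comparisons. They are not. The Analytic Plan first estimates one proportion per ad among participants as a whole, its second goal concerns the ads themselves, and its third concerns characteristics other than use status. The point covers the primary comparison and the per-ad tests of users against non-users.

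**There is no bias.** Random assignment makes ad mix independent of status in expectation, and group totals are monitored. This stands; the cost is variance only.

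**The size is mostly small.** With up to 10 ads per panel and no overlap, 10, 20 and 40 panels would mean up to 100, 200 and 400 ads, and nothing in the documents supports that scale. With 2-5 panels the ad-level effect is negligible. If ads were shared across panels, raters per ad would rise and the imbalance would shrink. The worst-panel figures describe an extreme, and other panels gain raters by the same chance. If users means current and ever users together (2,350 against 1,175), K = 20 gives +1.4% and a smallest cell of about 45. All of this stands and limits the point to a minor one. It does not remove it, because the ad-mix component in Step 4 does not depend on the number of panels and the remedy needs no extra data.

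**Conclusion.** The point holds as a minor improvement in design and reporting. The plan does not tie panel assignment to a variable that it already holds and that defines its primary comparison. If assignment is simple randomisation, the average loss at ad level is below 1% of variance for up to 10 panels and reaches about 4% only at 40. The worst-served ad loses more, with an interval 6% wider at 10 panels and 19-22% wider at 40. The pooled status contrast carries about 1% to 12% avoidable variance if the panel-mean SD is 0.1 to 0.3 and the within-panel SD is 0.8.

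These sizes rest on assumed numbers of panels, equal panel probabilities, no sharing of ads between panels, and assumed SDs. The documents fix none of these. The missing number of panels and missing target of raters per ad are what prevent a firmer figure.

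**What to change.** In the Design section, state the number of panels, the number of ads in each and the intended raters per ad in each status group. Assign panels at random within current, ever and never users, by permuted blocks or least-filled-first. If the survey program already does this, say so.

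In the Analytic Plan, add panel or ad to the pooled model, so that chance ad-mix differences are adjusted for and the standard errors reflect the balance.

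The cost is likely to be one setting in the survey program and a few sentences of text, with no added respondents and no added time for participants. Balance will not be exact: the exclusions for too few answered items or too short a completion time act after assignment, so the analysed cells will still differ slightly.

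### The panel is a two-stage area sample of households, but the planned tests and model allow for dependence only within a person; this affects mainly the precision of overall means and ad-level proportions, and the comparison by use status only slightly.

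*Combined protocol and SAP*

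**What the plan says.** Subjects Selection Criteria describes how the panel was built: "This is conducted through a two-stage sampling process". On the first stage: "The first stage is the primary sampling unit, which is a National Frame Area of an entire metropolitan area or county". The secondary sampling "units are segments defined from Census tracts or block groups". The unit recruited is the household: "Selected households are invited to join" the panel.

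On who is approached, the Design section says "All panel members aged 18-65 will be invited to be screened", and Subjects Selection Criteria repeats it: "For this study, all 18-65 year old panel members will be screened". No rule limits participation to one person per household. The Design section also says "we estimate a random sample of 22,000 adults will be screened to achieve our goal of 3,000 completed surveys", and the Sample Size section likewise refers to a random sample of about that number. The two descriptions are not reconciled.

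In the Analytic Plan, the ad-level comparison is: "Chi-squared tests will compare proportions between CBD users and non-users". The pooled analysis is a random-effects logistic regression, and the stated purpose of its random effect is to handle several ratings from one person. Tests are two-sided at 0.05 in SAS 9.4. The plan names no survey procedure, strata, cluster variable, robust variance, or area or household effect.

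**The concern.** People in the same county, tract or household tend to resemble one another, and here that could apply both to CBD use and to how an ad is read. If the analysis treats them as independent, the effective sample size is overstated and standard errors are too small. The study presents itself as a national probability sample meant to inform regulation, so its stated precision should reflect how the sample was drawn.

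The Analytic Plan is not silent on dependence. It identifies one level, ratings within a person, and handles it, while the sampling description documents further levels that it leaves out. The point concerns standard errors only. Whether estimates should be weighted is a separate question.

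**Working it through.** **The plan's own figures.** The documents state no power, precision or design effect, so there is no such figure to reproduce. The 22,000 is a field-yield figure. The nearest reconstruction is 1,000 / (0.34 × 0.14) = 21,009, which is 4.5% below 22,000. Nothing below depends on it.

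**Inputs from the documents.** Sample size 3,525 (Design); two-stage area sample of households (Subjects Selection Criteria); two-sided 0.05 tests (Analytic Plan).

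**Inputs assumed.** Number of areas K = 50 to 200; intracluster correlations as shown; completed surveys per household h = 1.0 to 1.5. The documents give none of these.

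**1. A single mean or proportion, area clustering.** DEFF = 1 + (m − 1)ρ, with m = 3,525 / K.

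| K | m | ρ = 0.001 | ρ = 0.005 | ρ = 0.01 | ρ = 0.02 |
|---|---|---|---|---|---|
| 50 | 70.5 | 1.07 | 1.35 | 1.70 | 2.39 |
| 100 | 35.25 | 1.03 | 1.17 | 1.34 | 1.69 |
| 200 | 17.625 | 1.02 | 1.08 | 1.17 | 1.33 |

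The effective sample size, 3,525 / DEFF, runs from 3,467 down to 1,475. Correct standard errors exceed the naive ones by a factor of √1.017 = 1.01 to √2.39 = 1.55.

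**2. A single ad.** Each participant is randomised to a panel of up to 10 ads. If a fraction f of the sample rates a given ad, m becomes f × m. The documents do not give f. For illustration, with K = 50 and f = 1/4, m = 17.625, and at ρ = 0.02 the DEFF is 1 + 16.625 × 0.02 = 1.33 instead of 2.39.

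**3. Comparison by use status.** The relevant inflation is the Moulton form, DEFF = 1 + (m − 1)ρxρy, where ρx is the intracluster correlation of use status and ρy that of the outcome. The true size of a nominal 5% test is 2[1 − Φ(1.96/√DEFF)].

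- Area, ρx = 0.01 to 0.05, ρy = 0.005 to 0.02: from 1 + 16.625 × 0.01 × 0.005 = 1.001 to 1 + 69.5 × 0.05 × 0.02 = 1.07. Size 5.0% to 5.8%.
- Household, ρx = 0.3, ρy = 0.1 to 0.5, replacing m by h: from 1.00 (h = 1.0) to 1 + 0.5 × 0.3 × 0.5 = 1.075 (h = 1.5). Size 5.0% to 5.9%.
- Household extreme, ρx = 1 (members always share use status), h = 1.5, ρy = 0.5: 1 + 0.5 × 1 × 0.5 = 1.25. Size 8.0%.

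These ranges take area and household one at a time. Adding the top of both ordinary ranges gives 1 + 0.0695 + 0.075 = 1.14, a size of about 6.7%. That requires every assumption to be at its upper end together.

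**The case against.** The strongest reply is that the primary question is perception by use status, and for that comparison the effect nearly vanishes. Users and non-users live in the same areas, so most of the shared variation cancels. Where people from one cluster fall in different use groups, the naive test errs on the conservative side. This stands, and it sets the size of the point.

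A reader might infer that the use-status tests run at 8% to 11%. Such figures come from applying a design effect of 1.25 or 1.5, suited to a single estimate, to a comparison. Under the ranges above, 8.0% needs complete sharing of use status within households, and nothing here gives 11% for these tests.

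A reader might also infer that several members of a household will respond. The documents do not show this. They do not say how many people per household join or respond, and the random-sample wording competes with the statement that all members are invited. A random draw would be expected to reduce household overlap but would leave area clustering in place.

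Finally, the Analytic Plan specifies no confidence intervals, so poor coverage cannot be charged to a stated analysis. It does, however, plan ad-level proportions and overall means, and any standard error or interval reported with them would carry the fault. That the actual programs might use survey procedures is possible, but nothing in the plan says so.

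**Conclusion.** The gap is real: area clustering is documented and no stated method accounts for it. Household clustering is possible but not shown. The consequence falls mainly on the precision of overall means and ad-level proportions, which bear on the plan's second goal, identifying which claims are read in prohibited ways. For the primary comparison by use status it is minor, under one percentage point of test size when area or household clustering is taken alone under the ordinary assumptions.

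All these figures rest on assumed cluster counts and correlations and on formulas that treat clusters as equal in size. They show a plausible order of magnitude and do not estimate what this panel would give. The point justifies a change because the remedy is cheap. It does not suggest that the main conclusions are at risk.

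**What to change.** 1. Request masked primary sampling unit (PSU), stratum and household identifiers from the panel operator.
2. For ad-level proportions and tests, use PROC SURVEYFREQ with STRATA and CLUSTER statements and the Rao-Scott chi-squared test. For means of claim type, safety and appeal, use PROC SURVEYMEANS or SURVEYREG. Clustering at PSU level also covers households and repeated ratings.
3. For the pooled analysis, keep the random-effects logistic model and use sandwich standard errors with the PSU as the independent unit. Alternatively, report a survey logistic model as a sensitivity analysis, noting that its odds ratios are population-averaged and so differ in meaning from those of the random-effects model.
4. State whether all panel members or a random sample will be invited, and whether more than one person per household may take part.
5. If identifiers cannot be supplied, say in the report that intervals and p-values do not reflect the sampling design and may be too narrow. Selecting one respondent per household is not a substitute: the analyst cannot do it without household identifiers, and it leaves area clustering untouched.

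The cost is a data request, different procedures in the SAS version already named, and somewhat wider intervals, mainly for overall means and proportions. The sampling, questionnaire and fieldwork need not change.

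### The 1-to-5 claim ratings are reduced to yes/no at an unstated cut for the ad-level proportions and the logistic regression; an ordinal mixed model with all four cumulative proportions is a cheap improvement

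*Combined protocol and SAP*

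**What the plan says.** Under Outcome Measure(s), claim perception is named as the primary outcome, to be examined "by CBD use status. We will determine if advertisements are interpreted by consumers in one or more ways that the FDA has determined are prohibited". It is measured by six items, "all of which will use a 5-point response scale, (1) Not at all to (5) Extremely". Only the two end points are labelled.

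The Analytic Plan then has three steps.

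1. Pooled over ads: "First, analyzing all claims together, we will assess the mean score for each claim type", with the purpose "to determine if CBD use status is associated with interpreting ads as containing one of the prohibited claim types". This step uses the full scale. It names no test or model.
2. Per ad: "we will then estimate the proportion of participants that interpret the claim as one or more of the prohibited claim types". "Chi-squared tests will compare proportions between CBD users and non-users".
3. Pooled over ads again: "we will model the likelihood of interpreting a claim as a prohibited claim type as a function of CBD use status" and other covariates, "using random-effects logistic regression modeling to account for the repeated measures within an individual". The resulting odds ratios are to identify differences between groups.

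No section gives the rating at which a participant is taken to have interpreted an ad as prohibited. None of the three steps is named as primary.

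**The concern.** Steps 2 and 3 need a yes/no outcome, but the data are five-level ratings. Four cuts are possible (2, 3, 4 or 5 and above), and the plan is compatible with each.

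The stakes differ between the two steps. Goal 2 is to identify which claims consumers read in prohibited ways, and it rests on the ad-level proportions. There the cut can decide whether a prohibited reading is a majority or a minority finding, and a cut chosen after the ratings are seen cannot be told apart from one chosen for its result. Goal 3, on participant characteristics, rests on the regression. There the main cost is precision, because a binary split ignores differences among ratings on the same side of the cut. An ordinal form of the same model uses all five levels and needs no cut.

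**Working it through.** The plan gives no power, effect size, standard deviation or expected proportion for these outcomes, so there is no stated figure to reproduce. What follows is illustration.

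**Inputs from the documents:** a 1-5 scale, six items, up to 10 ads per person, about 1,000 people per use-status group, two-sided 0.05.

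**Assumptions:** two rating spreads over 1 to 5, even (20% each) and skewed (40/25/17/11/7%); ICC 0.3-0.5; exactly 10 ads per person.

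**1. Share counted as yes.** This is the sum of the category shares at or above the cut. It gives 80/60/40/20% for even ratings and 60/35/18/7% for skewed ratings.

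**2. One or more of the six items.** Assuming an underlying normal rating for each item and a between-item correlation of 0.3, the share with at least one item at or above the cut is 99.5/96/85/61% for even ratings and 96/81/57/29% for skewed ratings.

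**3. Information kept by a binary split, relative to a proportional-odds model.** With q the share counted as yes and p_k the category shares,

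eff = [1 − q³ − (1 − q)³] / [1 − Σp_k³].

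The denominators are 1 − 5(0.008) = 0.96 (even) and 1 − 0.0862 = 0.9138 (skewed).

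| Cut | Even: q | eff | Skewed: q | eff |
|---|---|---|---|---|
| ≥2 | 0.80 | 0.48/0.96 = 0.50 | 0.60 | 0.72/0.9138 = 0.79 |
| ≥3 | 0.60 | 0.72/0.96 = 0.75 | 0.35 | 0.6825/0.9138 = 0.75 |
| ≥4 | 0.40 | 0.75 | 0.18 | 0.4428/0.9138 = 0.48 |
| =5 | 0.20 | 0.50 | 0.07 | 0.1953/0.9138 = 0.214 |

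**4. Effect on use-status contrasts.** These compare people, and each person contributes about 10 ratings, so only the within-person part of the variance is inflated:

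ratio = [ICC + (1 − ICC)/(10·eff)] / [ICC + (1 − ICC)/10].

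- eff 0.50: ICC 0.3 gives 0.44/0.37 = 1.19; ICC 0.5 gives 0.60/0.55 = 1.09.
- eff 0.75: 1.06 and 1.03.
- eff 0.79: 1.05 and 1.02.
- eff 0.48: 1.20 and 1.10.
- eff 0.214: 0.6275/0.37 = 1.70 and 0.734/0.55 = 1.33.

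So the increase is about 2-20% at every cut except the top cut with skewed ratings, where it is 33-70%. The formula treats the ICC as unchanged by the split, which is an approximation.

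**5. Does the odds ratio itself move?** Take a uniform latent shift of 0.15 SD between groups (assumption), applied to even, low-skewed (40/25/20/10/5%) and mirror-image high-skewed ratings. The odds ratio stays within about 1.27-1.40 over all cuts. Suppose instead that the groups have equal means of 3.0 but different spread (15/20/30/20/15% against 25/15/20/15/25%, assumed). The odds ratio is then 0.53, 0.81, 1.24 and 1.89 at the four cuts, so its direction reverses.

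**The case against.** The strongest reply is that the primary outcome is claim perception by use status, and the first analysis answers that with mean scores, which need no cut. This stands. A reader might infer that the study's headline result hangs on the cut, or that the plan throws the ratings away. The documents support neither: the full scale is kept for goal 1, and no analysis is named primary. What remains is that the mean-score step names no test and does not address goal 2 or goal 3.

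Second, the regression odds ratio need not depend on the cut. Under proportional odds it is the same at every cut, and step 5 above shows little movement under a uniform shift. The reversal comes from a constructed example in which proportional odds fails, and there a single ordinal odds ratio would mislead as well. This stands, and it is why the fix needs a fallback.

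Third, a reader might infer that comparisons between ads suffer most from the lost information. The plan contains no ad-against-ad contrast, so that loss falls on nothing planned.

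Fourth, goal 2 is a yes/no question and will always need a cut. That is right. The ordinal model does not replace the cut there, and one model per claim type does not produce the one-or-more composite.

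Fifth, the word logistic does not exclude an ordinal model. However, next to proportions and the likelihood of interpreting a claim as a given type, binary is the natural reading. If ordinal was meant, the plan should say so.

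**Conclusion.** The point holds for the ad-level proportions, their chi-squared tests and, on its natural reading, the random-effects logistic regression. All three use a yes/no outcome whose cut is stated nowhere.

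For goal 2 the dependence is large: the same even ratings give anything from 80% to 20% for a single item. For the regression the issue is efficiency, not bias, unless proportional odds fails. The loss for use-status contrasts is modest at most cuts and becomes substantial only if a high cut is applied to ratings concentrated at the low end.

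Every size given here rests on assumed rating spreads, ICC and item correlation, because the documents supply none. The direction does not: an unstated cut leaves the ad-level result open, and under proportional odds a binary split of a five-level rating keeps less information than the ordinal model. This is a worthwhile and inexpensive improvement; it does not invalidate the study.

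**What to change.** - **Regression.** Fit a cumulative-logit mixed model to the 1-5 rating, one per claim type, with the planned covariates and random effects (PROC GLIMMIX in the SAS 9.4 already specified). Check proportional odds, and report cut-specific odds ratios if it fails.
- **Ad-level results.** For each ad and claim type, report the cumulative proportions at all four cuts. Name one cut for the planned proportions and chi-squared tests.
- **Combination rule.** State how the items form the one-or-more outcome. Outcome Measure(s) lists the youth and science items as separate types, while the proportion step merges them.
- **Timing.** Fix the cut and the rule before any ratings are examined. Masking use status alone would not be enough, because a cut could still be chosen from the pooled ratings.
- **Sensitivity.** Keep the binary logistic model at the named cut.
- **Hierarchy.** Say whether the mean-score or the regression analysis is primary.

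The cost is SAP wording and a change of distribution and link in the same software; no new data are needed. The downside is a proportional-odds assumption to check and a slightly less direct yes/no reading of the regression.
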